5 STUDY ENROLLMENT AND WITHDRAWAL

Sixty males and non-pregnant females, 18-45 years old, inclusive, who are in good health and meet all eligibility criteria, will be enrolled from a single Vaccine and Treatment Evaluation Unit (VTEU) site. The target population should reflect the community at large at the participating VTEU site. Estimated time to complete enrollment in this trial is approximately 5 months. Information regarding this trial may be provided to potential subjects who have previously participated in vaccine trials conducted at the participating VTEU site. Other forms and/or mechanisms of recruitment may also be used. The local Institutional Review Board (IRB) will approve all materials prior to use.

Subject Inclusion and Exclusion Criteria must be assessed by a study clinician licensed to make medical diagnoses and listed on the Form FDA 1572 as the site principal investigator or sub-investigator.

No exemptions are granted on Subject Inclusion/Exclusion Criteria in DMID-sponsored studies. Questions about eligibility will be directed toward the DMID Medical Officer.

5.1. Subject Inclusion Criteria

Subjects eligible to participate in this study must meet all of the following inclusion criteria:

1. Provide written informed consent before initiation of any study procedures.
2. Are able to understand and comply with planned study procedures and be available for all study visits/phone calls.
3. Males or non-pregnant females ages 18-45, inclusive.
4. Subject must have a body mass index (BMI) ≥ 18.5 and $< 35 \text{ kg/m}^2$.
5. Are in good health*

* *As determined by medical history and physical examination to evaluate acute or currently ongoing chronic medical diagnoses or conditions, defined as those that have been present for at least 90 days which would affect the assessment of the safety of subjects or the immunogenicity of study vaccinations. Chronic medical diagnoses or conditions should be stable for the last 60 days (no hospitalizations, ER or urgent care for condition and no adverse symptoms that need medical intervention such as medication change/supplemental oxygen). This includes no change in chronic prescription medication, dose, or frequency as a result of deterioration of the chronic medical diagnosis or condition in the 60 days prior to enrollment. Any prescription change that is due to change of health care provider, insurance company, etc., or that is done for financial reasons, as long as in the same class of medication, will not be considered a deviation of this inclusion criterion. Any change in prescription medication due to improvement of a disease outcome, as determined by the site principal investigator or appropriate sub-investigator, will not be considered a deviation of this inclusion criterion. Subjects may be on chronic or as needed (prn) medications if, in the opinion of the site principal investigator or appropriate sub-investigator, they pose no additional risk to subject safety or assessment of reactogenicity and immunogenicity*

and do not indicate a worsening of medical diagnosis or condition. Similarly, medication changes subsequent to enrollment and study vaccination are acceptable provided there was no deterioration in the subject's chronic medical condition that necessitated a medication change, and there is no additional risk to the subject or interference with the evaluation of responses to study vaccination. Note: Topical, nasal, and inhaled medications (apart from steroids as outlined in the Subject Exclusion Criteria), herbals, vitamins, and supplements are permitted.

6. Oral temperature is less than 100.0 °F (37.8°C).
7. Pulse is 47 to 105 beats per minute (bpm), inclusive.
8. Systolic blood pressure (BP) is 85 to 150 mm Hg, inclusive.
9. Diastolic blood pressure (BP) is 55 to 95 mm Hg, inclusive.
10. Have acceptable screening laboratories^{#&} within 28 days prior to enrollment (Refer to [Appendix C](#) for acceptable screening values.)

[#] Screening labs include white blood cell (WBC), Hgb, platelet count, ANC, sodium, potassium, creatinine, albumin, total protein, PT, PTT, alanine aminotransferase (ALT). Blood Urea Nitrogen (BUN) will be obtained only if creatinine is above normal range.

[&] Screening laboratory values that are outside the range of eligibility but are thought to be due to an acute condition or due to laboratory error may be repeated once. [see Manual of Procedures (MOP)]

11. Have normal screening laboratories for urine protein. Trace protein is acceptable.
12. Drug screen for opiates is negative.
13. Hemoglobin A1C (HgbA1C) <6.3% at screening.
14. HIV 1/2 antibody negative.
15. HCV antibody negative.
16. HBsAg negative.
17. Women of childbearing potential[‡], must be using an effective method of contraception[§] from 30 days prior to the first study vaccination until 90 days after the second study vaccination.

[‡] *Not sterilized via tubal ligation, bilateral oophorectomy, hysterectomy, successful Essure® placement (permanent, non-surgical, non-hormonal sterilization) with history of documented radiological confirmation test at least 90 days after the procedure (or with use of another birth control method if history of confirmation test not confirmed), still menstruating, or < 1 year of the last menses if menopausal.*

[§] *Includes, but is not limited to, non-male sexual relationships, abstinence from sexual intercourse with a male partner, monogamous relationship with a vasectomized partner, male condoms with the use of applied*

spermicide, intrauterine devices, NuvaRing®, and licensed hormonal methods such as implants, injectables or oral contraceptives (“the pill”).

18. Women of childbearing potential must have a negative serum pregnancy test at screening and a negative urine pregnancy test within 24 hours prior to each study vaccination.
19. Women agree to not donate eggs (ova, oocytes) from the start of screening onwards until at least 90 days after the second vaccination.
20. Agrees not to participate in another clinical trial during the study period.
21. Agrees not to donate blood to a blood bank for 3 months after receiving the second study vaccine.

5.2. Subject Exclusion Criteria

Subjects eligible to participate in this study must not meet any of the following exclusion criteria:

1. Women who are pregnant, planning to become pregnant or lactating*.
** Includes breastfeeding or planning to breastfeed at any given time from the receipt of study vaccination through the 6-month trial period.*
2. Known allergy or history of anaphylaxis, severe local or other serious adverse reactions to vaccines or vaccine products%, or history of severe allergic reactions.
% Includes a known allergy to egg, egg products and aminoglycosides or any of the constituents of the study vaccines [e.g., polysorbate 80, ethylenediaminetetraacetic acid (EDTA), L-histidine, tris (hydroxymethyl)-amino methane (THAM)].
3. Received an experimental agent⁵ within 3 months prior to Day 1, or expects to receive an experimental agent⁶ during the 6-month trial-reporting period.
⁵ Including vaccine, drug, biologic, device, blood product, or medication.
⁶ Other than from participation in this study.
4. Received immunoglobulin or other blood product within 3 months before enrollment in this study.
5. Received any licensed live vaccine within 30 days prior to the first study vaccination through 30 days after the second study vaccination.
6. Received a licensed inactivated vaccine within 14 days prior to the first study vaccination through 14 days after the second study vaccination.
7. Has been vaccinated with an Ebola vaccine.

8. Has been diagnosed with Ebola disease, or exposed to Ebola virus including travel to West Africa[^] in 2014-2016.

[^] *West Africa includes but is not limited to the countries of Guinea, Liberia, Mali, Nigeria, and Sierra Leone.*

9. Known or suspected receipt of ChAd3-EBO-Z or other ChAd3-vectored vaccine.

10. Known or suspected receipt of an adenovirus serotype 5 (Ad5)-based vaccine.

11. Known or suspected receipt of any licensed or investigational small pox (vaccinia)-based vaccine[#].

[#] *Includes any MVA-based candidate vaccine (Imvamune or Imvanex), Dryvax, or Acam2000.*

12. Has a typical vaccinia scar.

13. Confirmed Asplenia/Functional Asplenia.

14. A history of bleeding or clotting disorders.

15. Thyroidectomy or thyroid disease requiring medication during the last 12 months.

16. History of chronic urticaria (recurrent hives).

17. Individuals in whom the ability to observe possible local reactions at the eligible injection sites (left and right deltoid region) is, unacceptably obscured due to a physical condition or permanent body art.

18. Have an acute illness[#], as determined by the site PI or appropriate sub-investigator, within 72 hours prior to study vaccination.

[#] *An acute illness which is nearly resolved with only minor residual symptoms remaining is allowable if, in the opinion of the site PI or appropriate sub-investigator, the residual symptoms will not interfere with the ability to assess safety parameters as required by the protocol. Subjects may re-screen after an acute illness is resolved.*

19. Any confirmed or suspected immunosuppressive or immunodeficient condition* or use of anticancer chemotherapy or radiation therapy (cytotoxic) within 3 years prior to study vaccination

** including HIV infection.*

20. Administration of chronic (defined as more than 14 days) immunosuppressants or other immune modifying drugs within 6 months of receipt of study vaccine.

21. Have taken oral or parenteral (including intraarticular) corticosteroids of any dose within 30 days prior to study vaccination.

22. Have taken high-dose³ dose inhaled corticosteroids within 30 days prior to study vaccination.

³ High-dose defined using the inhaled high-dose reference chart ([Appendix B](#)).

23. Have a history of convulsions or encephalomyelitis within 90 days prior to study vaccination.
24. Current or past history of alcohol or drug abuse in the last 5 years.
25. Subjects with autoimmune disorders, chronic inflammatory disorders or neurological disorders with a potential autoimmune correlation.
26. Have any diagnosis, current or past, of schizophrenia, bipolar disease, or other psychiatric diagnosis that may interfere with subject compliance or safety evaluations.
27. Have been hospitalized for psychiatric illness, history of suicide attempt, or confinement for danger to self or others within 10 years prior to study vaccination.
28. Have received any antiviral within 3 days of study vaccination
29. History of myocarditis, pericarditis, cardiomyopathy, transient ischemic attack or stroke, myocardial infarction, angina, coronary artery disease, congestive heart failure, clinically significant arrhythmia*
** including any arrhythmia requiring medication, treatment, or clinical follow-up.*

30. Electrocardiogram (ECG) with clinically significant findings.*

** Clinically significant findings include the following:*

- a. Conduction disturbance (complete left or complete right bundle branch block or nonspecific intraventricular conduction disturbance with QRS ≥ 120 ms, PR interval ≥ 210 ms, any second- or third-degree atrioventricular block, or prolongation of the QT interval corrected according to Bazett's formula [$QTcB$] [> 450 ms]).*
- b. Significant repolarization (ST-segment or T-wave) abnormality.*
- c. Significant atrial or ventricular arrhythmia; frequent atrial or ventricular ectopy (e.g., frequent premature atrial contractions, 2 premature ventricular contractions in a row).*
- d. ST-elevation consistent with ischemia or evidence of past or evolving myocardial infarction*

31. A diagnosis of Type I or II diabetes. (A history of isolated gestational diabetes is not an exclusion criterion).
32. Current employee or staff paid entirely or partially by the contract for this trial, or staff who are supervised by the PI or Sub-Investigators.
33. Any condition that would, in the opinion of the Site Investigator or appropriate sub-investigator, is a contraindication to study participation.*

** Including acute or chronic (persisting for at least 90 days) clinically significant medical disease or condition, that would place the subject at an unacceptable risk of injury, render the subject unable to meet the*

requirements of the protocol, or may interfere with the evaluation of responses or the subject's successful completion of the study.

5.3. Eligibility Criteria for Dose 2

Subjects may not receive subsequent vaccination if any of the criteria in [Section 5.4.3](#) are met. The second vaccination may be deferred until eligibility criteria, as defined in [Section 5.4.3](#), are met (see [section 5.4.3](#)).

5.4. Treatment Assignment Procedures

5.4.1. Randomization Procedures

Per International Council for Harmonisation of Technical Requirements for Pharmaceuticals for Human Use (ICH) guideline E6: Good Clinical Practice (GCP), screening records will be kept at the participating VTEU site to document the reason why an individual was screened, but failed trial entry criteria. The reasons why individuals failed screening will be recorded in the Statistical and Data Coordinating Center's AdvantageEDCSM (Electronic Data Capture System).

Once consented and upon entry of demographic data and confirmation of eligibility for this trial, the subjects will be enrolled. Subjects will be randomized 1:1:1 in double-blind fashion to 1 dose of ChAd3-EBO-Z vaccine at Day 1 followed by a booster of placebo, ChAd3-EBO-Z (homologous), or MVA-BN®-Filo (heterologous) at Day 8.

Enrollment of subjects will be done online using the enrollment module of AdvantageEDCSM. The randomization code will be prepared by statisticians at the SDCC and included in the enrollment module for this trial. AdvantageEDCSM will assign each subject to a treatment arm after the demographic and eligibility data have been entered into the system. A designated individual at the participating VTEU site will be provided with a code list for emergency unblinding purposes, which will be kept in a secure place.

Instructions for use of the enrollment module are included in the AdvantageEDCSM User's Guide. Manual back-up randomization procedures and instructions are provided for use in the event that a participating VTEU site temporarily loses access to the Internet or the online enrollment system is unavailable.

Subjects who sign the informed consent form (ICF) and are randomized but do not receive study vaccine may be replaced. Subjects who sign the informed consent form, and are randomized and vaccinated, and subsequently withdraw, or are withdrawn or terminated from this trial, or are lost to follow-up may be replaced.

5.4.2. Masking Procedures

This is a double-blind clinical trial. Subjects, investigators, study personnel performing any study-related assessments following study vaccine administration, and laboratory personnel performing antibody assays will be blinded to treatment arm assignment (i.e., type of booster). Laboratory personnel performing experimental assays including antibody assays will also be masked to subject ID and study visit.

The randomization scheme will be generated by the SDCC and provided to unblinded study personnel (i.e., research pharmacists performing study vaccination preparations and unblinded study vaccine administrators) at the participating VTEU site. To preserve blinding and mask the color of study product in the syringe, the unblinded site research pharmacist will place a blinding tape or overlay on the syringe to mask its content. The vaccine will then be sent to an unblinded study vaccine administrator for administration to the subject.

The unblinded study vaccine administrator is a study personnel member credentialed to administer vaccines and may also participate in dose preparation, but will not be involved in study-related assessments or have subject contact for data collection following study vaccine administration.

The Safety Monitoring Committee (SMC) may receive data in aggregate and presented by treatment arm. The SMC may also be provided with expected and observed rates of the expected AEs in an unblinded fashion, and may request the treatment arm be unblinded for an individual subject if required for safety assessment. The SMC will review grouped and unblinded data in the closed session only. Refer to the protocol-specific Manual of Procedures (MOP) for unblinding procedures.

5.4.3. Discontinuation of Study Product

There are several reasons why a study subject may be prevented from receiving the second vaccination. If a subject's study vaccine must be discontinued before the end of the vaccination schedule, this will not result in automatic withdrawal of the subject from the study.

The second study vaccination will not be administered to a subject if any of the following criteria are met:

- Pregnancy
- Receipt of disallowed licensed vaccine, experimental product or medication (see [Section 5.2](#))
- New onset of illness or condition that meets the Exclusion Criteria (see [Section 5.2](#))
- Medical condition or medication change for which continued participation, in the opinion of the site principal investigator or appropriate sub-investigator, would pose a risk to the subject or would likely confound interpretation of the results. Note: Medication changes subsequent

to the first study vaccination are not exclusionary for receipt of the follow-up study vaccination provided there was no deterioration in the subject's chronic medical condition that necessitated a medication change, and there is no additional risk to the subject or interference with the evaluation of responses to study vaccination.

- Presence of signs or symptoms that could confound or confuse assessment of study vaccine reactogenicity.

Note: for subjects with transient injection site or systemic signs or symptoms, or with an acute illness, including an oral temperature greater than or equal to 100.0°F, follow-up study vaccination/s should be postponed/deferred until signs, symptoms, or acute illness have resolved, or are improving as further specified below. No study vaccine will be given outside the protocol-specified window.

Note for afebrile, acute illness only: If a subject is afebrile, his/her acute illness is nearly resolved with only minor residual symptoms remaining, this occurs within the acceptable protocol-specified window for that visit, and, in the opinion of the site principal investigator or appropriate sub-investigator, the residual symptoms will not interfere with the ability to assess safety parameters as required by the protocol, the subject may receive the follow-up study vaccination without DMID Medical Officer approval.

- Grade 3 solicited or unsolicited adverse event that is ongoing, whether or not it is improved or resolving. An unresolved or continuing Grade 1 or Grade 2 adverse event is permissible following the documented determination by the site principal investigator or appropriate sub-investigator, that it would not render study vaccination unsafe or interfere with the evaluation of adverse events or immunologic response.
- Grade 3 solicited or unsolicited adverse event that occurs in the 7 days following study vaccination, lasts for more than 24 hours without decreasing to a Grade 1 or Grade 2, and does not have an alternative etiology.
- Any laryngospasm, bronchospasm, or anaphylaxis within 1 day after administration of study product that is considered related to study product.
- Any generalized urticaria within 3 days after administration of study product that is considered related to study product.
- Serious adverse event related to the study vaccination.
- As deemed necessary by the site principal investigator or appropriate sub-investigator for noncompliance or other reasons.
- Subject refusal of further study vaccination.

- Termination of this trial.
- New information becomes available that makes further administration of the study vaccine unsafe.

Subjects who receive the first study vaccine but not the second vaccination will be encouraged to remain in this trial for follow-up, safety and immunogenicity assessments per [Appendix A: Schedule of Study Procedures and Evaluations](#). If the scheduled visit does not include collection of blood for safety or immunogenicity, the visit may be conducted by phone call/ electronic communication (e.g., email, text message) rather than in person continuing through approximately 6 months after the first study vaccination. See the protocol-specific Manual of Procedures (MOP) for alternate follow-up requirements.

Every attempt will be made to follow all adverse events, including solicited local site and systemic AEs, unsolicited non-serious adverse events, SAEs and MAAEs ongoing at the time of early withdrawal through resolution as per applicable collection times defined for the specific type of adverse event.

5.4.4. Study Withdrawal

Subjects may voluntarily withdraw their consent for trial participation at any time and for any reason, without penalty. The site principal investigator or appropriate sub-investigator may also choose to remove a subject from the study. A subject may withdraw or be withdrawn from this trial for any of the following reasons:

- Medical disease or condition, or any new clinical finding for which continued participation, in the opinion of the site principal investigator or appropriate sub-investigator, would compromise the safety of the subject, or would interfere with the subject's successful completion of this trial, or would interfere with the evaluation of adverse events or immunologic response.
- As deemed necessary by the site principal investigator or appropriate sub-investigator for noncompliance or other reasons.
- Subject withdrawal of consent.
- Subject lost to follow-up.
- Subject dies.
- Termination of this trial.
- New information becomes available that makes further participation unsafe.

In the case of subjects who fail to appear for a follow-up safety assessment, extensive effort (i.e., three documented contact attempts via phone calls, emails, text messages, etc., made on separate occasions and followed by a certified letter) will be made to locate or recall them, or at least to determine their health status. These efforts will be documented in the subject's study records.

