9. SAFETY EVALUATION

All safety analyses will be presented using the safety population. Any medical condition that is present at the time that the subject is screened will be considered baseline and not reported as an AE, unless it worsens in severity or increases in frequency during the study. When calculating the incidence of solicited and unsolicited adverse events (i.e., on a per subject basis), each subject will be counted once and any repetitions of solicited and unsolicited adverse events within a subject will be ignored; the denominator will be the number of subjects in the safety analysis population unless results are shown by dose in which case the denominator will be the number of subjects that received the respective dose.

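### Investigator removal under Protocol 5.4.4 for a finding that interferes with evaluation ends collection of new safety events, and the full Safety Population denominator then counts those later events as absent

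*Protocol*

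**What the plan says.** **Removal from the trial.** Protocol 5.4.4 states: "The site principal investigator or appropriate sub-investigator may also choose to remove a subject from the study". The first listed ground is a disease, condition or new clinical finding that, in the investigator's opinion, would compromise the subject's safety, hinder successful completion, "or would interfere with the evaluation of adverse events or immunologic response". A second ground is open-ended: "As deemed necessary by the site principal investigator or appropriate sub-investigator for noncompliance or other reasons".

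**Stopping vaccine only.** Protocol 5.4.3 lists reasons for not giving the second dose. They include a condition or medication change that "would pose a risk to the subject or would likely confound interpretation of the results", and the same noncompliance ground. When only the vaccine is stopped, "this will not result in automatic withdrawal of the subject from the study". Subjects who miss Dose 2 are encouraged to remain, and visits without safety or immunogenicity blood may be done by telephone or electronically.

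**After withdrawal.** Protocol 5.4.3 promises every attempt to follow events "ongoing at the time of early withdrawal through resolution as per applicable collection times defined for the specific type of adverse event". Under 5.4.5 the Early Termination Visit is encouraged, not required; 7.5 describes it as a single contact.

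**Outcomes and analysis.** The primary outcomes (Protocol 3.2.1) include vaccine-related unsolicited AEs through 28 days after the second vaccination, and SAEs and vaccine-related MAAEs through 6 months after the first. SAP 6.3.1 keeps everyone with at least one vaccination in the Safety Population. SAP 9 says of AE incidence that "the denominator will be the number of subjects in the safety analysis population unless results are shown by dose". SAP 6.5 leaves missing data missing.

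**The concern.** A new clinical finding after vaccination is the kind of information that the primary objective exists to capture. Making it a ground for leaving the trial can tie missing follow-up to having had a clinical event. Once Dose 2 has been given there is no vaccination left to withhold, so removal on the interference ground can then only end data collection. The question still arises at that stage: Protocol 7.3.3 and 7.3.4 have sites review interim history for continued eligibility at visits and calls after Dose 2.

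At stake is whether the unsolicited AE, SAE and vaccine-related MAAE counts cover the windows they are labelled with. The SAP describes no person-time summary and no sensitivity analysis for early withdrawal in the safety data. With 20 subjects per arm, one subject is 5 percentage points.

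**Working it through.** The plan has no power calculation or expected withdrawal rate to reproduce, so the check has three parts.

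**1. Is there any route by which a new event after removal is collected?**

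- Follow-up under 5.4.3 covers events already ongoing at withdrawal.
- The encouragement to remain in 5.4.3 is for subjects who missed Dose 2, not for those removed under 5.4.4.
- The Early Termination Visit (7.5) captures events up to that visit.
- The repeated contact attempts in 5.4.4 are for subjects who fail to appear, not for those taken out.
- Reporting after trial completion (9.3, 9.3.1) depends on the investigator becoming aware, and covers only SAEs suspected to be related.

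None of these systematically collects a new event arising after removal.

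**2. How much of each window is forgone?** Inputs: first vaccination on Day 1, final visit on Day 182 (7.4), Dose 2 on Day 8.

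SAE/MAAE window = 182 − 1 = 181 days; share forgone = (182 − day of removal) / 181.

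- Day 15: (182 − 15)/181 = 167/181 = 92%.
- Day 36: (182 − 36)/181 = 146/181 = 81%.

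Unsolicited AE window: Day 1 to Day 8 + 28 = Day 36, which is 35 days. Removal at Day 15 forgoes 36 − 15 = 21 of 35 days (60%); removal at Day 36 forgoes none.

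**3. What does the denominator do?** Assume that w subjects in an arm of 20 are removed and that no event of a given type has been seen in the arm. The values of w are assumptions. Intervals are exact (Clopper-Pearson) 95%; with no events the upper limit is 1 − 0.025^(1/n).

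| w | As planned | Removed subjects excluded | Each had a later, unseen event of this type |
|---|---|---|---|
| 1 | 0/20, upper 16.8% | 0/19, upper 17.6% | 1/20 = 5.0% (0.1–24.9) |
| 2 | 0/20, upper 16.8% | 0/18, upper 18.5% | 2/20 = 10.0% (1.2–31.7) |
| 3 | 0/20, upper 16.8% | 0/17, upper 19.5% | 3/20 = 15.0% (3.2–37.9) |

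The denominator alone moves the upper limit by 0.8 to 2.7 points. If two removed subjects are also replaced, as 5.4.5 allows, the planned result becomes 0/22 with an upper limit of 15.4%. The last column is a bound, not an estimate: it needs a new event after removal in a category where the subject was not already counted. SAP Tables 27 and 28 carry such intervals for unsolicited AEs. For SAEs and vaccine-related MAAEs, Table 23 gives only counts and percentages, and Tables 30 and 31 are listings.

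**The case against.** A reader might infer that removed subjects count as event-free. The documents do not support that. Protocol 9.2.4 requires every observed or reported event to be recorded, and the Early Termination Visit records events again. SAP 9 counts each subject once, so someone removed because of an AE is already in the numerator for that event. For the same reason, one removal does not by itself turn 1/20 into 0/20. Protocol 9.4 also follows SAEs and MAAEs to resolution beyond the reporting period.

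The SAP does not hide all missing data either. By-dose solicited tables use recipients of that dose, Table 26 has not-reported rows for several symptoms, Table 35 has a missing column, and the antibody tables show the number with valid results. SAP 7.1 provides a flowchart by arm, and Listing 2 gives each early termination with reason and study day. In a trial of 60, a removal would be visible.

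The 92% and 81% are calendar time. By Day 36 the unsolicited AE window, scheduled safety laboratory tests and ELISA draws are complete; two calls and one visit remain. The wording in 5.4.4 is permissive, the trial is for estimation only, and Protocol 11.4.5 expects little missing data.

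All of this stands, and it narrows the point to later, new events. It does not remove it: Tables 23 and 27 to 29 have no missing category, and a list of terminations shows that follow-up stopped, not what happened afterwards.

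**Conclusion.** The point holds in a limited form. For a vaccinated subject whom the investigator removes because a finding interferes with evaluation, new unsolicited AEs, SAEs and vaccine-related MAAEs are not systematically collected for the rest of their windows, and the full denominator treats them as absent. Any resulting error in those rates is downward. Per removed subject, 92% (Day 15) or 81% (Day 36) of the SAE/MAAE window is forgone, assuming the scheduled days and final contact on Day 182. Total bias cannot be sized, because the documents give no number of such removals.

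Two further inferences are not supported. Bias that differs by arm is conjecture: the investigators making the decision are blinded to the booster (Protocol 5.4.2). Nor do the documents show that removed subjects are the ones who separate ITT from PP. Later samples are lost, but PP also excludes out-of-window visits, missed second doses and disallowed products, none of which requires removal.

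This is a low-cost improvement to a primary outcome, not a flaw that invalidates the safety analysis.

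**What to change.** - **Reconcile Protocol 5.4.3 and 5.4.4** so that interference with evaluation is not by itself a reason to end safety follow-up.
- **State the follow-up rule in 5.4.4.** Any vaccinated subject removed by the investigator who has not withdrawn consent continues AE follow-up to the end of its window and SAE/MAAE follow-up through Day 182. The contacts already scheduled in 7.3.3, 7.3.4 and 7.4 are used, by telephone if visits or blood draws stop. Because this covers any investigator removal, the noncompliance and completion grounds need not be deleted.
- **Handle interference in the analysis** through the PP exclusions in SAP 6.3.3. These already name disallowed vaccines, corticosteroids and immunosuppressants; a line for an interfering medical condition would need adding.
- **If such removals have already occurred,** footnote Tables 23 and 27 to 29 with the number per arm who left before the window closed.

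The subject-safety ground and the investigator's discretion over vaccination are unchanged. The cost is protocol wording and a few telephone contacts per removed subject: three after Day 36 (Days 76, 106 and 182), or six after Day 15 (adding Days 22, 29 and 36). No subjects or assays are added.
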